### 6.1.2 Administration of CMP-001

If possible, the full volume should be injected into a single progressing lesion and as appropriate for the subject's dose cohort. If the full volume cannot be injected within the tumor, then the remaining drug volume should be injected into a second accessible tumor, if present. If the full volume still cannot be administered into the tumor then peritumoral injection of any remaining volume is acceptable.

If over time an injected tumor is clearly responding to therapy (eg, regresses below the minimum size that can readily be injected with the required volume), or if in the judgment of the Investigator, the subject cannot tolerate continued injections in that lesion because of local injection site reaction or other issues, then the injection may instead be administered intratumorally into a different progressing tumor lesion, or peritumorally at the original site or at a new tumor lesion.

If a single lesion is the only injectable lesion and decreases or disappears over time, we plan to continue injecting into the tumor bed for the entire 7 weeks (+) course of treatment and until first radiological assessment. If after the first radiological assessment at week 7, there is no tumor site available for injection, we plan to continue with Pembrolizumab +/- injection to tumor bed until progression, toxicity or if in the investigator's opinion continued treatment is in subject's best interest.

CMP-001 should be injected using aseptic technique. Use of topical and/or local anesthetic is permitted. For administration of CMP-001 a single cutaneous insertion point should be used and multiple needle tracks within the tumor should be injected until the full volume has been instilled.

The information on dose, volumes, and numbers of sites injected will be recorded for analysis.

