### **6.2.2 Pembrolizumab-Associated Adverse Events**

AEs associated with pembrolizumab exposure may represent an immunologic etiology. These immune-related AEs (irAEs) may occur shortly after the first dose or several months after the last dose of pembrolizumab treatment and may affect more than one body system simultaneously. Therefore, early recognition and initiation of treatment is critical to reduce complications. Based on existing clinical study data, most irAEs were reversible and could be managed with interruptions of pembrolizumab, administration of corticosteroids and/or other supportive care. For suspected irAEs, ensure adequate evaluation to confirm etiology or exclude other causes. Additional procedures or tests such as bronchoscopy, endoscopy, skin biopsy may be included as part of the evaluation. Based on the severity of irAEs, withhold or permanently discontinue pembrolizumab and administer corticosteroids. Dose modification and toxicity management guidelines for irAEs associated with pembrolizumab are provided in Table 7.

**Table 7 Dose modification and toxicity management guidelines for immune-related AEs associated with pembrolizumab monotherapy and IO Combinations**

General instructions:
 
 
1. Severe and life-threatening irAEs should be treated with IV corticosteroids followed by oral steroids. Other immunosuppressive treatment should begin if the irAEs are not controlled by corticosteroids.
 
2. Study intervention must be permanently discontinued if the irAE does not resolve or the corticosteroid dose is not <math>\leq 10</math> mg/day within 12 weeks of the last study intervention treatment.
 
3. The corticosteroid taper should begin when the irAE is <math>\leq</math> Grade 1 and continue at least 4 weeks.
 
4. If study intervention has been withheld, study intervention may resume after the irAE decreased to <math>\leq</math> Grade 1 after corticosteroid taper.
 
				
irAEs	Toxicity Grade (CTCAE v5.0)	Action With Pembrolizumab	Corticosteroid and/or Other Therapies	Monitoring and Follow-up

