## 7.0 TRIAL FLOW CHART

Procedure or Assessment	Screening (Day -21 to -1) a	W1 D1	W2 D1	W3 D1	W4 D1	W5 D1	W6 D1	W7 D1	W10 D1	Every 3 Weeks Post W10 (W13, W16 etc.)	End of Treatment b	30 Day Follow up visit n	Long Term Survival Follow-up o
CMP-001 Dose Number	n/a	1	2	3	4	5	6	7	8	9+	n/a	n/a	n/a
Visit Windows	n/a	n/a	±2 days	±2 days	±2 days	±2 days	±2 days	±2 days	±7 days	±7 days	±7 days	±7 days	± 1 month
Informed Consent	X												
Eligibility Criteria Assessment	X												
Medical History, Demographics, Cancer History including Prior Cancer Medications	X												
Physical Exam c	X	X		X	X			X	X	X	X		
Vital Signs d	X	X	X	X	X	X	X	X	X	X	X		
ECOG Performance Status	X	X		X	X			X	X	X	X		
Body Weight	X	X			X			X	X	X	X		
Height	X												
Electrocardiogram (ECG) e	X	X		X				X			X		
Autoimmune lab panel f	X										X		
Clinical Laboratory Tests (hematology, serum chemistry, urinalysis) g	X	X	X	X	X	X	X	X	X	X	X		
Coagulation Tests (PTT & INR) h		X						X	X	X			
Thyroid Function Tests	X			X				X			X		
Research blood Samples i	X	X		X			X		X	-			
Tumor Biopsy j	X			X			X		X	-			
Urine Pregnancy Test k	X	X			X			X	X	X	X		
Disease Assessment (PET-CT/CT) a, l	X	At W7D1 (or two cycles) and then as clinically indicated											
Adverse Event Monitoring n		Assessed continually from W1D1 through EOT +30 days											
Concomitant Medications		Assessed continually from 28 days prior to first CMP-001 dose through EOT +30 days											
CMP-001 dosing m		X	X	X	X	X	X	X	X	X			
Pembrolizumab Dosing		Pembrolizumab will be given according to pembrolizumab label (every 3 week)											

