**Footnotes for Trial Flow Sheet:**

- a. Computed tomography (CT neck/chest/abdomen/pelvis with contrast) or PET-CT scans may be performed  $\leq 3$  weeks prior to first CMP-001 dose but up to 4 weeks will be acceptable. MRI will only be considered in specific situation if needed.
- b. End-of-treatment (EOT) assessments to be performed within 7 days following removal of subject from CMP-001 treatment. Removal of a subject from CMP-001 treatment is defined as the time in which the Investigator decides to discontinue CMP-001 treatment for a subject.
- c. A full physical exam will be conducted at Screening and EOT. The Screening physical exam may be performed up to 72 hours prior to the Week 1 Day 1 (W1D1) visit. If the full physical exam is performed  $>72$  hours prior to the W1D1 visit, then a brief (symptom directed) physical exam must be performed within 72 hours prior to initiation of CMP-001.
- d. For the first five CMP-001 dosing visits, vital signs are to be collected prior to CMP-001 dosing, and at 30 ( $\pm 15$ ) minute intervals for 4 hours post end of CMP-001 dosing. Based upon the discretion of the Investigator, observation periods can be reduced to 1 hour for individual subjects who demonstrate mild to no adverse events. Reduced observation periods can be implemented only after the 6th dose of CMP-001. Vital signs should be performed prior to collection of clinical laboratory tests when they are performed at the same visit. On days that CMP-001 and Pembrolizumab are both given, vital signs should be collected following the administration of CMP-001. When CMP-001 intratumoral injection and pembrolizumab dosing fall on the same day, it is recommended that CMP-001 intratumoral injection precede pembrolizumab dosing.
- e. Electrocardiograms (ECGs) should be obtained at Screening and prior to CMP-001 intratumoral injection at the 1st, 3rd, and 7th CMP-001 injection (on W1D1, W3D1, W7D1), and EOT visit.
- f. Autoimmune lab panel to be collected at Screening and EOT. Table 9
- g. Clinical laboratory tests may be performed up to 72 hours prior to administration of CMP-001.
- h. Partial thromboplastin time (PTT) and international normalized ratio (INR) tests should be obtained, and results reviewed as per schedule above. These may be obtained up to 72 hours prior to administration of CMP-001.

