## 8.2 Assessing and Recording Adverse Events

An adverse event is defined as any untoward medical occurrence in a patient or clinical investigation participant administered a pharmaceutical product and which does not necessarily have to have a causal relationship with this treatment. An adverse event can therefore be any unfavorable and unintended sign (including an abnormal laboratory finding, for example), symptom, or disease temporally associated with the use of a medicinal product or protocol-specified procedure, whether or not considered related to the medicinal product or protocol-specified procedure. Any worsening (i.e., any clinically significant adverse change in frequency and/or intensity) of a preexisting condition that is temporally associated with the use of the Merck's product, is also an adverse event.

Changes resulting from normal growth and development that do not vary significantly in frequency or severity from expected levels are not to be considered adverse events. Examples of this may include, but are not limited to, teething, typical crying in infants and children and onset of menses or menopause occurring at a physiologically appropriate time.

Merck product includes any pharmaceutical product, biological product, device, diagnostic agent or protocol-specified procedure, whether investigational (including placebo or active comparator medication) or marketed, manufactured by, licensed by, provided by or distributed by Merck for human use.

Adverse events may occur during the course of the use of Merck product in clinical trials, or as prescribed in clinical practice, from overdose (whether accidental or intentional), from abuse and from withdrawal.

- All AEs from Week 1 Day 1 (treatment initiation) through 30 days following cessation of study treatment must be reported by the investigator.
- All AEs meeting serious criteria, from the time of treatment allocation/randomization through 90 days following cessation of study treatment, or 30 days following cessation of study treatment if the participant initiates new anticancer therapy, whichever is earlier must be reported by the investigator.
- All pregnancies and exposure during breastfeeding, from the time of treatment allocation/randomization through 120 days following cessation of study treatment, or 30 days following cessation of study treatment if the participant initiates new anticancer therapy must be reported by the investigator.

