**Routine Adverse Event Reporting**

For non-serious Adverse Events, documentation must begin after the subject signs the Informed Consent Document until 30 days after the last dose of CMP-001. Collected information should be recorded in the electronic/Case Report Forms (eCRF/CRF) for that subject. A description of the event, its severity or toxicity grade (according to [NCI's Common Toxicity Criteria \(CTCAE\)](#)),

onset and resolved dates (if applicable), and the relationship to the study drug should be included. Documentation should occur in real time. The principal investigator has final responsibility for determining the attribution of the event as it is related to the study drug.

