### Serious Adverse Event Reporting

For any experience or condition that meets the definition of a serious adverse event (SAE), recording of the event must begin after signing of the informed consent and continue through the 30 days after the last dose of CMP-001.

Investigators must report to the DSMC any serious adverse events (SAE), whether or not they are considered related to the investigational agent(s)/intervention (21 CFR 312.64). SAEs must be reported via an OnCore SAE Report within 24 hours of learning of the event.

An adverse event is considered **serious** if it results in ANY of the following outcomes:

1. Death
2. A life-threatening adverse event
3. An adverse event that results in inpatient hospitalization OR prolongation of existing hospitalization for  $\geq 24$  hours
4. A persistent or significant incapacity or substantial disruption of the ability to conduct normal life functions
5. A congenital anomaly/birth defect.
6. Important Medical Events (IME) that may not result in death, be life threatening, or require hospitalization may be considered serious when, based upon medical judgment, they may jeopardize the patient or subject and may require medical or surgical intervention to prevent one of the outcomes listed in this definition. (FDA, [21 CFR 312.32](#); [ICH E2A](#) and [ICH E6](#)).

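### The AE and SAE collection windows contradict each other: the flow chart and Appendix E count from CMP-001, Sections 5.5, 8.1.7.4 and 8.2 from study treatment

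*Combined protocol and SAP*

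**What the plan says.** **Counted from CMP-001.** Flow-chart footnote b: "End-of-treatment (EOT) assessments to be performed within 7 days following removal of subject from CMP-001 treatment". It dates removal from the investigator's decision to stop CMP-001. The AE row of the Section 7.0 flow chart reads "Assessed continually from W1D1 through EOT +30 days", and the concomitant-medication row ends at the same point. Footnote n places the safety follow-up 30 days after the EOT visit. Appendix E has non-serious AEs documented "until 30 days after the last dose of CMP-001", and has SAE recording "continue through the 30 days after the last dose of CMP-001".

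**Counted from study treatment.** Section 8.2: "All AEs from Week 1 Day 1 (treatment initiation) through 30 days following cessation of study treatment must be reported by the investigator". For SAEs the period is "from the time of treatment allocation/randomization through 90 days following cessation of study treatment", reduced to 30 days if new anticancer therapy starts. Section 8.2.3.1 repeats the 90 days. Section 8.1.7.4 times the safety visit from the last dose of study treatment and follows SAEs to 90 days. Section 5.5 places EOT assessments after study treatment has stopped. Section 5.4.1 counts concomitant medications from the last dose of trial treatment.

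**In between.** Footnote n allows SAEs 90 days from the end of treatment, but footnote b gives that term a CMP-001 meaning.

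**The two drugs can stop at different times.** If no site is left to inject after the week 7 scan, Section 6.1.2 says "we plan to continue with Pembrolizumab +/- injection to tumor bed until progression, toxicity". Section 6.2 allows one drug alone to be modified for toxicity more clearly related to it. Section 5.5 caps pembrolizumab at 35 treatments.

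**The concern.** If both drugs always stopped together, the choice of anchor would hardly matter for AEs. The protocol foresees that they may not. A CMP-001 anchor then closes AE collection during continuing exposure to the other study drug, whose immune-related events, according to Section 6.2.2, "may occur shortly after the first dose or several months after the last dose of pembrolizumab treatment".

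The anchor also governs scheduled tests. After W7D1 the flow chart schedules thyroid function tests only at EOT, and the autoimmune panel only at Screening and EOT. Under footnote b both can be finished while pembrolizumab goes on.

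At stake is the first secondary objective, the safety profile of the combination. If the source a site follows decides how long events are collected, patients with the same exposure can contribute different lengths of safety follow-up, and a descriptive AE table would not show it.

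**Working it through.** **Inputs.** Pembrolizumab every 3 weeks (Section 6.1.3), at most 35 treatments (Section 5.5); average treatment length 6 months (Section 1.0); W7D1 = day 43; Appendix E window of 30 days; Section 8.2 windows of 30 days (AE) and 90 days (SAE). The CMP-001 stop date is an assumption, so a range is shown.

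**The plan's own figure.** Section 5.5 equates 35 treatments with about 2 years. 35 × 21 = 735 days = 105 weeks = 2.01 years, which agrees.

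**Formulas.**
- Pembrolizumab dose k falls on day 1 + 21(k − 1). Dose 9 is on day 169 (about 6 months) and dose 35 on day 715.
- Appendix E cut-off = last CMP-001 day + 30.
- AE gap = (last pembrolizumab day + 30) − cut-off.
- SAE gap = (last pembrolizumab day + 90) − cut-off = AE gap + 60, if no new anticancer therapy starts.

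| Last CMP-001 dose | Pembrolizumab doses | Appendix E cut-off | Doses after cut-off | AE gap (days) | SAE gap (days) |
|---|---|---|---|---|---|
| With the last pembrolizumab dose (day 715) | 35 | day 745 | 0 | 745 − 745 = 0 | 60 |
| W7D1 (day 43) | 9 | day 73 | 5 | 199 − 73 = 126 | 186 |
| W25D1 (day 169) | 35 | day 199 | 25 | 745 − 199 = 546 | 606 |
| W13D1 (day 85) | 35 | day 115 | 29 | 745 − 115 = 630 | 690 |
| W7D1 (day 43) | 35 | day 73 | 31 | 745 − 73 = 672 | 732 |

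**Flow chart instead of Appendix E.** For a W7D1 stop with EOT 7 days later, AE monitoring closes on day 43 + 7 + 30 = 80, again with 31 of 35 doses still to come. Footnote n's 90-day SAE period, read with footnote b, closes on day 43 + 7 + 90 = 140, with 28 of 35 doses to come.

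**Section 8.2 followed.** With all 35 doses given, AE collection runs to day 745 and SAE collection to day 805, whenever CMP-001 stopped. No study-drug exposure is left out.

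**The case against.** The strongest reply is that Section 8.2 already has it right. It is worded as an obligation, and Section 8.1.2.1 sends the reader there for detail on recording AEs. Appendix E is the institution's monitoring plan; its SAE text concerns reports to the monitoring committee, and a shorter committee window does not cancel a longer protocol duty. Section 8.2 also requires a drug-related SAE that comes to the investigator's attention to be reported at any time. A site that follows Section 8.2 loses nothing.

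Much of this stands, and it rules out three stronger readings.

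- *That the plan as a whole cuts off toxicity during continued pembrolizumab.* The documents do not support this. Sections 5.5, 8.1.7.4, 8.2 and 8.2.3.1 all count from study treatment, so loss depends on which text is followed.
- *That responders are selectively under-observed.* A patient whose only injectable lesion has disappeared could be affected more, but this is an inference. Section 6.1.2 allows tumor-bed injection to continue, which keeps the CMP-001 anchor open. CMP-001 may also be stopped alone for toxicity, so those affected need not be responders. Patients in complete response may stop treatment (Sections 5.5 and 8.1.6.1), which shortens any gap.
- *That a gap of 90 weeks or more is to be expected.* That is a worst case: CMP-001 stopped at Week 7, all 35 pembrolizumab doses given, and Section 8.2 not followed.

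What the reply does not remove is the conflict. A pointer to Section 8.2 is not a statement that it overrides the flow chart or Appendix E, and the flow chart is what the protocol uses to set visit procedures. The any-time rule covers only drug-related SAEs that happen to be reported; it does not cover non-serious AEs, and events are not actively sought.

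**Conclusion.** The point holds as an internal contradiction with a practical consequence. Two operational sources, the flow chart and Appendix E, count from CMP-001; Sections 5.5, 8.1.7.4, 8.2 and 8.2.3.1 count from study treatment. Following the former as written would end AE collection during continuing pembrolizumab.

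The AE gap ranges from 0 to 672 days according to the assumed CMP-001 stop date and number of pembrolizumab doses; at about the stated average treatment length, with a W7D1 stop, it is 126 days. Separately, Appendix E and Section 8.2 differ by 90 − 30 = 60 days in the length of the SAE window, even when both drugs stop together, except where new anticancer therapy brings Section 8.2 down to 30 days.

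The DLT window is 15 days from W1D1, so dose finding and the primary objective are untouched. The secondary safety objective is affected. The plan should be corrected on this point, but it does not undermine the design.

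**What to change.** Bring the other texts into line with Section 8.2, and define cessation of study treatment once, as the last dose of whichever study drug is stopped later. Then change:

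- footnote b, so that EOT follows the end of study treatment, as in Section 5.5;
- footnote n, so that the safety visit and the 90-day SAE period use that same date;
- the flow-chart AE and concomitant-medication rows;
- both Appendix E reporting sections: 30 days for AEs and 90 days for SAEs, keeping Section 8.2's existing exception for new anticancer therapy.

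Specifying the later-stopped drug matters, because a phrase such as the last dose of either drug could be read as the earlier one.

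The cost is protocol wording and some additional AE recording at pembrolizumab visits that already take place. A 30-day AE window will still miss non-serious immune-related events that arise months after the last dose. This change removes the contradiction and keeps collection open during exposure; it does not extend late follow-up beyond what Section 8.2 already provides.

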## **8.0 TRIAL PROCEDURES**

### **8.1 Trial Procedures**

The Trial Flow Chart - Section 7.0 summarizes the trial procedures to be performed at each visit. Individual trial procedures are described in detail below. It may be necessary to perform these procedures at unscheduled time points if deemed clinically necessary by the investigator.

Furthermore, additional evaluations/testing may be deemed necessary by the Sponsor and/or Merck for reasons related to participant safety. In some cases, such evaluation/testing may be potentially sensitive in nature (e.g., HIV, Hepatitis C, etc.), and thus local regulations may require that additional informed consent be obtained from the participant. In these cases, such evaluations/testing will be performed in accordance with those regulations.

#### **8.1.1 Administrative Procedures**

##### **8.1.1.1 Informed Consent**

Consent must be documented by the participant's dated signature or by the participant's legally acceptable representative's dated signature on a consent form along with the dated signature of the person conducting the consent discussion.

A copy of the signed and dated consent form should be given to the participant before participation in the trial.

The initial informed consent form, any subsequent revised written informed consent form and any written information provided to the participant must receive the IRB/ERC's approval/favorable opinion in advance of use. The participant or his/her legally acceptable representative should be informed in a timely manner if new information becomes available that may be relevant to the participant's willingness to continue participation in the trial. The communication of this information will be provided and documented via a revised consent form or addendum to the original consent form that captures the participant's dated signature or by the participant's legally acceptable representative's dated signature.

Specifics about a trial and the trial population will be added to the consent form template at the protocol level.

The informed consent will adhere to IRB/ERC requirements, applicable laws and regulations and Sponsor requirements.

##### **8.1.1.2 Inclusion/Exclusion Criteria**

All inclusion and exclusion criteria will be reviewed by the investigator or qualified designee to ensure that the participant qualifies for the trial.

### **8.1.1.3 Medical History**

A medical history will be obtained by the investigator or qualified designee. Medical history will include all active conditions, and any condition diagnosed within the prior 10 years that are considered to be clinically significant by the Investigator. Details regarding the disease for which the participant has enrolled in this study will be recorded separately and not listed as medical history.

